5.4 Enrollment

We propose to enroll 96 participants in order to ensure complete data from 75 participants, assuming a very conservative 30% drop-out rate. We will monitor the dropout rate on an ongoing basis, and modify the number of participants recruited as needed to ensure a final sample of N = 75 study completers.

The study will enroll up to a total of 96 consecutive adults (aged \geq 18 years) with IC/BPS to participate in baseline and follow-up clinical assessment and quantitative sensory testing. Eligible participants will be randomized to an intervention (cognitive-behavioral self-management) or active control condition at a 2:1 rate. Following randomization, $\frac{2}{3}$ of participants will be provided with a cognitive-behavioral self-management intervention, and the other $\frac{1}{3}$ will engage in an active attention control condition. Those enrolled in the study will also be followed after the intervention time period of 8 weeks and again at 3 months.

The registration process will occur through VUMC either at the Osher Center for Integrative Medicine at Vanderbilt, located at [REDACTED], [name], online, or at the VUMC Clinical Research Center at [REDACTED], [name]. All participants will have a VUMC medical record identification number prior to beginning the study. Consenting will occur in-person or remotely where questions can be answered by a member of the research team, and assessment measures will be completed electronically on-site at VUMC or remotely online through a secure RedCap link. Consenting procedures will occur electronically in eConsent format online or on site using an electronic device where participants can fill out study measures online through RedCap. Psychophysical and Quantitative Sensory Testing will occur at the same site. After participants enroll in the study and complete their pre-treatment assessment, they will be randomized to the treatment or control condition.

For aims 2 and 3, we anticipate enrolling our first patient in the second half of the study’s first year. Given our recruitment strategies, we anticipate consistent enrollment of subjects in years 1 (N=10), 2 (N=43), 3 (N=43) of the project, peaking in years 2 and 3. We aim to reserve the majority of year 4 to conclude data collection and focus on data analysis, manuscript preparation, and additional grant

applications. Data cleaning and quality monitoring will occur following enrollment of our first subject throughout the end of year 4 of the award. The final year will focus primarily on data analysis, dissemination, and manuscript preparation.

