5. STUDY PROCEDURES

5.1 Overview

Participants will complete a total of three assessments before, immediately after, and 3 months following an 8-week period where they will either receive an 8-week series of psychosocial intervention or attention control visits. This equals a total of 11 visits with VUMC. Based on attrition rates from investigations in similar chronic pain conditions,³⁸ we will assume a conservative study dropout rate of 30%, and will recruit up to 96 participants in order to attain complete data on 75 subjects. In order to recruit 96 participants including follow-up we anticipate this study will occur over the course of three to four years. Below we detail a summary of the visit structure along with a figure indicating study flow.

The assessments corresponding to the study will occur in two stages at each of the three timepoints: (1) completion of patient-reported outcomes online, and optional (2) completion of psychophysical testing and the collection of biological samples in person at the CRC. Participants will have the option of enrolling in the first or both stages of these assessment visits, each of which will have separate consent forms.

Once patients pass the phone screen, they will be scheduled for a Study Enrollment visit, to take place remotely over the phone or online. They will present for a remote assessment visit to complete consenting procedures and will be sent patient-reported outcome measures online via REDCap. Those who elected to participate in in-person psychophysical testing procedures will then be scheduled for the CRC. Patients in the Study Enrollment Visit will complete separate consent forms corresponding to the online and in-person study procedures. The eligibility checklist will be reviewed again to ensure participants meet criteria and assessment battery will be given. Participants who enroll in the study will be randomized after the assessment (see section 5.3 for full description of randomization procedures).

Pretreatment visit (1, T0):

Once patients are screened and determined to be eligible to participate in the study, they will complete informed consent and an assessment battery remotely. If they agree to undergo psychophysical testing, they will be scheduled to do so at the **Clinical Research Center** (CRC) for their first pre-treatment assessment visit (procedures detailed below).

Visits (2-9, T1):

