5.10 Treatment discontinuation

As per standard clinical procedures, a participant will be withdrawn from the treatment intervention if:

- Noncompliance to protocol, including but not limited to:
 - Participant engages in behavior that is disruptive,
 - Participant engages in behavior that interferes with the appropriate administration of treatment
 - Participant does not attend scheduled sessions
- The study must close for any reason
- Intercurrent illness or condition that would, in the judgment of the PI and mentorship team (including multiple MDs), affect assessment of clinical status to a significant degree or require discontinuation of study treatment
- General or specific changes in the participant's condition render the participant unacceptable for further treatment in the opinion of the PI and mentorship team
- The subject desires to withdraw

Participants who are withdrawn from the study treatment intervention will be invited to complete study assessments during treatment, post-treatment, 3-month and 6-month follow-up in order to allow for complete data for the planned intent-to-treat analyses. Participants will receive payment for the time it takes to provide outcome data at each assessment point.

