5.11 Replacement of patients who discontinue early

The study intends that patients will complete the full 8 weeks of treatment. If a patient discontinues study treatment then that patient may be replaced with a new patient.

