9. STATISTICAL CONSIDERATIONS

9.1 Analytic Plan by Aim

Aim 1: To construct a patient-centered CBT self-management (SM) intervention specific to IC/BPS. Pre-work for this aim will include a theme analysis of coded transcripts from focus groups using NVivo 9 to code, analyze, and interpret transcripts using elements of grounded theory.⁷⁸ For the project period, this aim will primarily involve consolidating qualitative work and will use descriptive statistics where appropriate.

Aim 2: To obtain preliminary data comparing the effectiveness of integrating SM interventions into usual treatment (N = 50) to control (AC, N = 25) in improving targeted primary (symptom improvement [≥ 7 point reduction in GUPI]) and secondary (pain, distress, quality of life) outcomes.

Power and sample size considerations: ■ are comparing GUPI-Total Score, a continuous variable, between the SM group and a matched AC group with a 2:1 randomization scheme. The GUPI-Total Score tends to be normally distributed with a standard deviation of 8.61.^{47,79} A 7-point decrease in total GUPI score is considered clinically meaningful⁷⁹ and a robust assessment of response to treatment.⁴

Assuming a Type I error of 0.05 and power of .90, we will need 50 experimental subjects and 25 control subjects to reject the null hypothesis that the sample means of both treatment groups are equal post-treatment. ■ intend to have 50 experimental and 25 control subjects to obtain even groups for analytical purposes, as recommended by ■ DSBM. Given our use of statistical models, ■ power is increased when ■ appropriately adjust for covariates.

■ will test the hypothesis that those receiving the SM intervention will show improved outcomes relative to AC. ■ will use generalized linear mixed models to compare responses on the Genitourinary Pain Index (GUPI⁸⁰-Primary Outcome) between treatment groups, adjusting for baseline GUPI and covariates. As recent evidence recommends the examination of pain and urinary symptoms separately,²⁵ ■ will examine the GUPI pain subscale and GUPI urinary subscale separately in secondary analyses. ■ will perform one interim analysis at approximately 50% completion of data collection using the O'Brien-Fleming method to preserve alpha accounting for repeat testing.

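### Enrolling 96 at 30% dropout yields about 67 completers, not the 75 stated in sections 5.1 and 5.4

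*Combined protocol and SAP*

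**What the plan says.** Two sections link an enrolment number, a dropout rate and a completer target. Section 5.1: "we will assume a conservative study dropout rate of 30%, and will recruit up to 96 participants", with 75 subjects with complete data as the aim. Section 5.4: "We propose to enroll 96 participants in order to ensure complete data from 75 participants, assuming a very conservative 30% drop-out rate".

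Section 5.4 then describes monitoring of dropout, with a commitment to "modify the number of participants recruited as needed to ensure a final sample of N = 75 study completers". Its next paragraph sets a ceiling: "The study will enroll up to a total of 96 consecutive adults". The yearly forecast in the same section (10, 43 and 43) also adds up to 96.

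Two other provisions bear on the final number. Section 5.11: "If a patient discontinues study treatment then that patient may be replaced with a new patient". Section 5.10 invites participants withdrawn from the intervention to complete assessments "in order to allow for complete data for the planned intent-to-treat analyses".

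The target of 75 comes from the Aim 2 power statement in section 9.1: "we will need 50 experimental subjects and 25 control subjects to reject the null hypothesis". The primary model there compares GUPI between groups, "adjusting for baseline GUPI and covariates".

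**The concern.** The enrolment figure is presented as already containing a 30% allowance for dropout, and a generous one. It does not contain it: 96 covers about 22%. A team that believes 96 tolerates 30% would see no warning at 25% dropout, although 96 × 0.75 = 72 is already below target.

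The safeguards leave the outcome open. Top-up and replacement could each restore 75, but section 5.4 also gives 96 as a maximum and section 5.1 repeats it. Under the protocol's own dropout assumption these provisions collide. Whether the trial ends with 67 or 75 completers then depends on a rule that is not written down. What is at stake is a modest amount of power for the primary comparison and the accuracy of a stated design figure.

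**Working it through.** **Inputs.** Enrolment 96, dropout 30% and completers 75 (sections 5.1 and 5.4). Allocation 2:1 (section 5.3). GUPI total SD 8.61, 7 points as clinically meaningful, type I error 0.05, power 0.90, arms of 50 and 25 (section 9.1). Section 9.1 does not say that the test is two-sided or that the 7 points are a between-group difference. Both are inferred because they reproduce its arm sizes.

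**1. The base of 75 reproduces.** The normal approximation (two-sided 0.05, 90% power, 2:1) needs 24 AC and 48 SM; one-sided it would need only 20 and 40. For the t-test at 50:25 the noncentrality is (7/8.61)/√(1/50 + 1/25) = 0.813/0.245 = 3.32 on 73 df, which gives power of 90.6%. So 50:25 is sound.

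**2. The step from 75 to 96 does not reproduce.** Required enrolment = completers/(1 − dropout) = 75/0.70 = 107.1. By arm, 50/0.70 = 71.4, so 72, and 25/0.70 = 35.7, so 36; the total is 108. Multiplying instead of dividing gives 75 × 1.30 = 97.5, which is near 96 but not equal to it. That may be where 96 came from, but the protocol shows no derivation, so this is conjecture.

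**3. What 96 delivers.**
- Completers at 30% dropout: 96 × 0.70 = 67.2 (44.8 SM and 22.4 AC), a shortfall of 75 − 67.2 = 7.8, or about 8.
- Dropout that 96 can absorb: (96 − 75)/96 = 21/96 = 21.9%.
- If each participant independently has a 30% chance of dropping out, the probability of at least 75 completers out of 96 is about 5%.

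**4. The ceiling.** At 30% dropout, top-up or replacement must take enrolment to 108, which is 108 − 96 = 12 above the stated maximum. The yearly forecast is 10 + 43 + 43 = 96 and leaves no room for this.

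**5. Power if enrolment stops at 96.** Noncentral t, two-sided 0.05, difference 7, SD 8.61. The adjusted rows use SD × √(1 − r²) and 64 df, where r is the correlation between baseline and outcome GUPI. The documents do not give r, so a range is assumed.

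| Analysed SM:AC | Adjustment | Power |
|---|---|---|
| 50:25 | none | 90.6% |
| 48:24 | none | 89.4% |
| 45:22 | none | 86.8% |
| 45:22 | r = 0.2 | 88.1% |
| 45:22 | r = 0.3 | 89.7% |
| 45:22 | r = 0.4 | 91.9% |
| 45:22 | r = 0.5 | 94.5% |

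At 45:22, power reaches 90% at r of about 0.31. The interim analysis is not allowed for in any row.

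**6. Recovery through follow-up of dropouts.** Expected dropouts are 96 × 0.30 = 28.8. Recovering 7.8/28.8 = 27.1% of them, about 8 of 29, would bring the number analysed back to 75.

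**The case against.** The protocol does not rely on 96 alone. The sentence after the quoted one commits to adjusting recruitment until there are 75 completers, and section 5.11 allows replacement. The 67-completer result arises only if the ceiling overrides both. That is correct, and it is why the 67 and the 86.8% are conditional. But a figure said to cover 30% should need no top-up at 30%, and the text does not say which provision prevails.

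The 30% is a whole-study rate and section 5.1 covers the 3-month follow-up, while section 9.1 powers the post-treatment comparison. Losses by post-treatment may be smaller. If they were 25% (an assumption), 72 would be analysed (48:24), with unadjusted power of 89.4%. This stands: 67 is a lower bound for the post-treatment analysis at 30% study dropout. It does not rescue the statement about complete data, which is where the arithmetic fails.

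Dropout is not defined. If it meant leaving treatment only, participants followed under section 5.10 could still supply complete data. The wording about study dropout and study completers weighs against that reading, and no recovery rate is assumed anywhere.

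Section 4.1 reports excellent first-year retention, so 30% may be pessimistic. It gives no rate. If the true expectation is nearer 22%, the 30% is the figure to change. Finally, Aim 2 is described as obtaining pilot data and the loss of power is small. Both are fair, and they limit the weight of the point rather than its correctness.

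**Conclusion.** The concern holds. The figures 96, 30% and 75 are inconsistent on a plain reading: 96 enrolled gives about 67 completers at 30% dropout, and 75 completers at that rate needs 108. The arithmetic rests on no assumption beyond the protocol's own numbers, with dropouts counted as lacking complete data.

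The consequence is modest and conditional. If enrolment stops at 96 and all dropouts are lost to the primary analysis, unadjusted power is 3.8 points lower than at 50:25 (90.6 − 86.8). This assumes a two-sided test, a 7-point between-group difference and no allowance for the interim look. The planned baseline-adjusted model may still reach 90%. The 50:25 calculation is not in question, and nothing here points to bias or an inflated type I error. The text should be corrected because a stated sample-size figure is wrong and the rule that would resolve it is missing.

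**What to change.** 1. In sections 5.1 and 5.4, replace the sentence linking the three figures with wording such as: *Enrolling 96 yields 75 completers if no more than 21 (22%) drop out; at 30% dropout it yields about 67 (about 45 SM and 22 AC).*
2. State whether top-up under section 5.4 and replacement under section 5.11 may take enrolment above 96 and, if so, to what maximum. The number that matches 30% dropout and 75 completers is 108 (72:36). If the sponsor prefers to keep 96 as a firm limit, justify an expected dropout of about 22%, for example from the first-year retention data.
3. Optionally, add to section 9.1 that 67 completers gives about 87% unadjusted two-sided power for a 7-point difference, before any gain from baseline adjustment and without allowance for the interim analysis.

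The cost is protocol wording and a slightly less favourable stated figure. Twelve further participants are needed only if both 30% and 75 are kept.

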5.5 Retention

Our **retention strategy** will be informed by the PI's experience-to-date and mentor experience. We will track planned contacts and regular communication to improve data collection and promote study engagement. After initial screening, we will schedule regular follow-up contacts per study protocol including appointment reminders for follow-up. Planned contacts will occur through participants' preferred methods of either text, calling, or emailing. Moreover, a study interventionist interacts with every participant at each visit for an extended period of time, depending on the subject's group assignment. Participants are additionally provided with contact information for the PI and her study team to facilitate good communication.

Treatment phase

5.6.1 Psychosocial Self-Management (SM)

The psychosocial SM intervention consists of 8 weekly 50- minute individual visits with an assigned trained therapist. Sessions follow the content from a structured treatment protocol developed by the PI following a series of focus groups with the patient population (i.e. IRB #170653). Treatment modules are optimized from similar approaches toward chronic pain and tailored specifically to the condition based on voiced patient needs. Modules include relaxation training, pain coping strategies, IC/BPS and pain psychoeducation, and assertiveness skills. At the first visit, patient and provider will co-construct treatment goals, which will also affect the ordering of modules provided in the treatment to reflect the patient's primary needs. Therapists will follow a summarized session-by-session 'guide' to ensure they adhere to the major content of each session for fidelity monitoring purposes. Patients will be given a patient manual to coincide with treatment. The current therapist manual, therapist field guide, and patient treatment manual have been provided for IRB approval.

5.6.1.1 Intervention delivery adjustments and online access:

Due to infection precautions, in-visit restrictions may occur which could impact participants' ability to come on site. As such, we will conduct SM intervention visits to HIPAA-compliant videoconferencing platform (Zoom.us) for the duration of the SM intervention to prevent treatment interruption and trial delay.

Participants will be asked about their internet access during screening so that they can be properly scheduled. If a participant does not have a stable internet connection but desires to participate in the study, we will keep their contact information in the event that we elect to conduct in-person visits in the future.

5.6.2 Attentional Control (AC)

The AC will reflect a similar visit pattern as intervention sessions. Sessions will occur under the premise of monitoring symptoms and understanding lifestyle and health. Sessions will occur via scheduled

telephone calls and follow a structured procedure. In each phone call, the therapist will follow a script and orally administer and document responses from structured assessments inquiring about symptom patterns such as the Symptom and Healthcare Utilization Questionnaire³⁹, Self-Evaluation of Quality of Life,⁴⁰ and Ryff Scale of Psychological Wellbeing⁴¹. Selected content will reflect questions commonly asked at routine medical visits in urology, along with questions about general health and wellness. Participants attempting to discuss issues beyond the script will be told, “I’m sorry but as this is a research study, we need to focus on monitoring your current symptoms.” AC will control for patient contact to better isolate intervention effects.

5.6.3 Fidelity monitoring

The PI will oversee intervention training and delivery by adhering to NIH Behavioral Change Consortium guidelines⁴² recently reviewed as applied to clinical pain trials in Edmond (2018).⁴³ This will include structured training in intervention delivery, recording of sessions, and the PI engaging in weekly supervision with trial therapists to review content summary guide checklists and session material.

Clinical assessments

The battery of assessments below will be given at pretreatment, posttreatment, and at the three-month follow-up mark. Assessments will be completed in two stages at each timepoint: 1) online patient reported outcome measures and 2) in person psychophysiological testing and the collection of biological samples.

5.7.1 Patient-Reported Outcome measures

We selected measures that provide continuity between recently- reviewed pre-existing literature on IC/BPS, expert recommendations,⁴⁴ and results of ongoing trials.⁴⁵ Please see Protocol Table (**Appendix L**) for the timing of each measure as well as planned contacts.

Consent/eConsent

Patients will read and sign online consent form(s) written in accessible language outlining the potential treatment courses, risks and benefits, privacy, and the assessments and testing that will be performed. Consent forms will correspond to each of the two assessment stages: with one consent form to separately reflect in-person psychophysical assessment procedures. eConsent can be completed on REDcap.

Demographics

DEMO: Patients will complete a brief demographic questionnaire indicating items such as age, sex, gender, ethnicity, religious orientation, and household income. Patients will also indicate their diagnoses and information regarding diagnosis/treatment and medication use. The questionnaire will take approximately 3 minutes to complete.

Urologic Symptoms

GUPI⁴: The Genitourinary Pain Index (**GUPI-primary outcome**) is a 15-item symptom scale examining gender-specific pain, urinary symptoms, and quality of life impact. It is a validated and responsive instrument to assess symptom severity in both men and women with genitourinary pain complaints.⁴⁶ The

GUPI measures pain and urinary symptoms separately and cumulatively, reflecting IC/BPS assessment recommendations for clinical trials and takes <2 minutes to complete.⁴⁷

RICE⁴⁸: The RAND Interstitial Cystitis Epidemiology (RICE) scale is an 11-item self-report measure designed to identify women with IC/BPS symptoms and describe their symptoms, taking approximately 2 minutes to complete. This measure was developed using a rigorous, consensus-based protocol and validated against the current gold standard of clinical diagnoses by medical experts. It has demonstrated high specificity and sensitivity, and is recommended for prevalence-based studies⁴⁸. It takes <1 minute to complete.

Pain Experiencing

MBM-II⁴⁹: The Michigan Body Map-II (MBM-II) is a self-report measure used to assess the location(s) of chronic pain complaints and widespread body pain. It is a two-sided body image with check-box responses for 35 potential body areas where chronic pain (defined as pain > 3 months) might exist, and a box for “no chronic pain.” It takes 2-3 minutes to complete. In this study, the measure is being used as an indication of centralized pain and pain sensitivity. We will use an open source version of the body map created in Redcap for the Collaborative Health Outcomes Information Registry initiative.

Comorbidity

FS⁵⁰: the Fibromyalgia Symptom Scale is a 7-item questionnaire assessing modified 2010 American College of Rheumatology diagnostic criteria for fibromyalgia and includes a) an index of widespread pain and b) an index of symptom severity via patient self-report. This survey was designed by experts for epidemiologic study. It is administered with a pain body map. A total score on this scale ranges from 0-31, with scores ≥ 13 indicating a high likelihood of fibromyalgia. This scale takes approximately 3 minutes to complete.

MISCI⁵¹: The Multidimensional Inventory of Subjective Cognitive Impairment (MISCI) is a 10-item self-report measure assessing cognitive difficulties in fibromyalgia patients. Items address the past seven days and exist on a Likert scale of 1 to 5, with 5 indicating higher levels of cognitive impairment. The internal reliability and convergent validity of the item are dependable. The MISCI takes <1 minute to complete.

Quality of Life

FSFI⁵²: The Female Sexual Function Index (FSFI) is a 19-item questionnaire with six domains of female sexual functioning. It takes <2 minutes to complete.

IIEF^{53, 54}: The International Index of Erectile Dysfunction (IIEF) consists of 15 items and five domains pertinent to male sexual functioning. It has been studied in varied cultural contexts and translated into 10 languages. The item is reliable and valid, detecting clinical changes well. It takes <2 minutes to complete.

PISES⁵⁵: The Painful Intercourse Self Efficacy Scale (PISES) is a version of the Arthritis Self Efficacy Scale adapted to assess dimensions of sexual experience. It is an 8-item measure that contains items rating self-efficacy related to pain from sexual intercourse on a 10-point likert scale. Using this scale, ■ adapted wording to IC/BPS-relevant symptoms based on information gathered in patient interviews in a former investigation (#170653). This measure has been adapted for similar populations used in previous

investigations as a domain of sexual functioning not captured in traditional sexual dysfunction measures.⁵⁵

Affective Vulnerability

PROMIS-29 Scale^{56,57}: The Patient-Reported Outcomes Measurement Information System® (PROMIS®) was designed to develop, validate, and standardize item banks to measure key domains of physical, mental, and social health in chronic conditions. The PROMIS-29 scale consists of 29 items asking about specific symptoms related to pain, fatigue, function, and physical and emotional health. These scales have been developed by experts for use in clinical trials and validated across populations. [REDACTED] use an abbreviated form of this scale, excluding redundant questions covered by the PHQ-8 and GAD-7 described below. This scale takes approximately 4 minutes to complete.

PHQ-8⁵⁸: The eight-item Patient Health Questionnaire depression scale (PHQ-8) is established as a valid diagnostic and severity measure for depressive disorders in large clinical studies. It consists of 8 questions where participants indicate on a Likert scale the extent to which [REDACTED] have experienced symptoms of depression within the past two weeks, with 0 being “not at all” and 3 being “nearly every day.” It takes <1 minute to complete.

GAD-7⁵⁹: The Generalized Anxiety Disorder (GAD) questionnaire is a self-administered 7 item instrument that uses some of the DSM-V criteria for GAD to identify probable cases of GAD along with measuring anxiety symptom severity. It can also be used as a screening measure of panic, social anxiety, and PTSD. It was modeled after the PHQ-9 to be used quickly and effectively within a primary care setting.

PCL-5⁶⁰: The PTSD Checklist for the DSM-5⁶⁰ is a 20-item measure with a five-point Likert scale that assesses the presence of post-traumatic stress. It utilizes the symptom checklist for PTSD in the DSM-5 and inquires about trauma-induced thoughts and behaviors in the past month. The item takes about 5 minutes to complete.

Environmental/Social

THQ⁶¹: The Trauma History Questionnaire⁶¹ (THQ) is a 24-item self-report measure that examines experiences with potentially traumatic events such as crime, general disaster, and sexual and physical assault using a yes/no format. For each event endorsed, respondents are asked to provide the frequency of the event as well as their age at the time of the event. The THQ takes approximately 5-10 minutes to complete and has been determined to be reliable and valid in clinical and non-clinical samples⁶². This measure will be given in conjunction with the PCL-5 to provide an index trauma by which potential PTSD symptoms are related to. This measure will be given at baseline only.

Beliefs and Attitudes

CSQ-CAT⁶³ : The Coping Strategies Questionnaire- Catastrophizing scale (CSQ-CAT)⁶³ contains six questions and a seven-point Likert scale (from “never do that” to “always do that”) regarding the negative, escalating cognitions that patients can experience as a result of pain. It takes <1 minute to complete.

Treatment Response

PGI-C⁶⁴: Patient Global Impression of Improvement (PGI)⁶⁴ is a global index used to rate the response of a condition to an intervention. Patients rate their impression of change on a 7-point likert scale ranging

from “very much improved” to “very much worse.” This question is routinely used in clinical care and has been validated as a tool to assess perceived impact of disease management⁶⁵. This questionnaire will be given post-treatment and at follow-up only and takes <1 minute to complete.

Treatment Utilization

The Health Utilization Form, created by our lab, is a self-report questionnaire containing sixteen questions that pertain to care utilized during the five-month period of the study. This measure will be given at post-treatment and follow-up to gather further information about treatment utilization during the study period.

